## 5.3. Analysis Populations

### 5.3.1. Safety Population

All subjects who are enrolled and have taken at least 1 dose of study drug comprise the safety population. The safety population will be used to conduct all safety analyses, including baseline and demographics.

### 5.3.2. Intent-to-Treat Population

All subjects who are enrolled and have taken at least 1 dose of study drug constitute the intent-to-treat (ITT) population. All efficacy analyses will be conducted using the ITT population. It is noted that the ITT population is effectively identical to the safety population for this study.

### 5.3.3. Per-Protocol Population

The per-protocol (PP) population includes those subjects in the ITT population who are considered to be sufficiently compliant with the protocol. The PP population will be used for certain supportive sensitivity analysis of efficacy and safety. Derivation rules for PP population can be found in [Section 5.9.6](#).

## 5.4. Statistical Methodology

### 5.4.1. General Methodology

Unless otherwise denoted, SAS® procedures (Version 9 or above) will be employed for the generation of all tables, graphs, and statistical analyses.

Descriptive summaries for continuous variables will include, but not be limited to, the number of observations, mean, standard

deviation, median, minimum, and maximum. Descriptive summaries for categorical variables will include the number and percentage of subjects in each category.

The Safety Population will be used for all safety analyses, and the ITT population will be used for all efficacy analyses. The primary efficacy analysis will also be repeated by using the PP population. [REDACTED]

#### **5.4.2. Control of Type I Error**

All confidence intervals will be 95% and tests will be performed at 2-sided 0.05% level. Because of the exploratory nature of the study analyses, except for tests regarding the coprimary endpoints, no multiplicity adjustment will be performed. To control overall Type I error in testing hypotheses regarding the coprimary endpoints, a sequential testing procedure will be used.

- Step 1 will test the correlation between percent change from baseline in spleen volume at Week 24 and the last titrated dose level, and only if the null hypothesis of no correlation can be rejected, Step 2 will be carried out.
- Step 2 will test the correlation between percent change from baseline in total symptom score at Week 24 and the last titrated dose level. In case Step 1 fails to reject the null hypothesis, the inferential comparison (p-values) of Step 2 will still be generated for descriptive purposes only.

#### **5.5. Baseline Values**

A baseline value (for analysis purposes) is the last, non-missing measurement obtained during the screening visit and baseline visit unless otherwise stated, with the exception of laboratory values and the total symptom score. For laboratory assessments, values obtained on Day 1 (see Section 5.6) will be included in deriving baseline as the laboratory values are scheduled to be obtained before on-site administration of study drug. For total symptom scores, different derivation rules will be used (see [Section 5.9.2.2](#)).

#### **5.6. Day 1, Study Day, and Study Time Points**

Day 1 is the date of first dose of study medication.

The study day at a visit/reporting date will be calculated by the visit/reporting Date – Day 1 + 1. This study day will be subtracted by 1 if it is less than or equal to zero, so that a study day of zero will never occur. A study day of -1 indicates 1 day prior to Day 1.

Other study time points will use nominal weeks, such as Weeks 4, 8, 12, etc, according to the Schedules of Assessments (see [Table 2](#) and [Table 3](#)), as recorded on the CRF, regardless of the actual time windows these visits fall into, unless otherwise stated. This is especially true for analyses such as laboratory values and vital sign values where by-study-week summaries are to be generated, as well as for spleen palpation length over time summaries.

Exceptions to the statements about study time points described above include (but are not limited to) spleen volume at Week 24 (see [Section 5.9.1](#)), total symptom score at several major study time points (see [Section 5.6](#)), and final titrated dose level (see [Section 5.9.3.1](#)).

Another exception is related to spleen palpation length analysis. Per study CRF design, if a subject's EOT Visit coincides with a scheduled visit, then in database, only EOT Visit data will be available. So when a subject has spleen palpation length data collected on an "EOT Visit" (or End of Extension Phase Visit, as appropriate and if applicable), an effort will be made to see if the data actually falls into a scheduled visit, such as Weeks 4, 8, 12, 16, 20, 24 (treatment phase), 36, 48, 60, etc (extension phase) by using the window of Week of scheduled visit\*7 ± 5 days.

Following the situation described above, if EOT data contain spleen volume measurements and the situation is not resolved by the time of database lock, then similar effort will be made by treating spleen volume data labeled from "EOT Visit" as data collected from unscheduled visit. See [Section 5.9.1](#) for how spleen volume data from unscheduled visits will be used in the analysis.

The situation described above is not an issue of importance to other variables such as laboratory values, since in analyses by time point, "EOT" will be one of the time points to be displayed.

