9.4. End of Treatment (± 5 days)

If a decision is made that the subject will withdraw from study participation, the end-of-treatment visit (EOT) should be conducted. If the EOT Visit coincides with a regular study visit, the end-of-treatment evaluations will supersede those of that scheduled visit, the data should be entered in the end of treatment visit in the CRF. The subject should be encouraged to return for the follow-up visit. The following will be performed:

- Review concomitant medications.
- Review transfusion status.
- Record adverse events.
- Perform complete physical examination.
- Measurement of spleen length below the costal margin by palpation.
- Vital signs.
- MRI (or CT scan in applicable subjects) should only be performed at the EOT visit if the subject discontinues treatment **prior** to Week 24.
- Complete PGIC question ([Appendix 5](#)).
- ECOG status assessment.
- Perform study drug accountability assessment.
- Blood sampling for the following laboratory tests (see [Appendix 4](#)):
 - Serum chemistry tests
 - Hematology
 - Coagulation tests
 - Lipid panel
- 
- Contact IVRS to register subject discontinuation.

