12.2. Statistical Analyses

12.2.1. Primary Analyses

Co-Primary Endpoints:

- Correlation of % change in spleen volume at Week 24 compared to baseline versus final titrated dose.
- Correlation of % change in Total Symptom Score as measured by the modified MFSAF v2.0 diary at Week 24 compared to baseline versus final titrated dose.

The null hypothesis is that the correlation between percent change in spleen volume or total symptom score and final titrated dose is zero. The test will be based on the t test for a product-moment correlation coefficient:

$$t = r_{xy} \sqrt{(n - 2) / (1 - r_{xy}^2)}$$

(Cohen 1988, Formula 3.1.1)

A two-sided alpha of 5% will be used. With a sample size of 150, the critical correlation that is needed to reject H_0 is 0.16. If the absolute value of the observed correlation is 0.16 or higher, H_0 will be rejected. In order to keep the overall alpha at 5%, a sequential testing procedure will be used: First we will test the correlation with % change in spleen volume, and only if the null hypothesis of no correlation can be rejected will we continue to test the correlation with % change in Total Symptom Score.

Safety Endpoints:

Safety and tolerability will be assessed by monitoring the frequency, duration and severity of adverse events, performing physical examinations, collecting vital signs, collecting laboratory data for hematology, serum chemistry, coagulation parameters, and lipid panel through Week 156.

Change in platelet count from baseline to each visit where the variables are measured will be tabulated with summary statistics.

Proportion of subjects with new onset of Grade 4 thrombocytopenia events, and proportion of subjects with new onset of Grade 2 or higher hemorrhage, as measured by CTCAE will be tabulated with summary statistics. The hazard functions of time to onset of the above two safety measures will be estimated using life table method.

Adverse events will be tabulated by the Medical Dictionary for Regulatory Activities (MedDRA[®]) preferred term and by system organ class. Severity of AEs will be based on the CTCAE scale as indicated in [Section 11.1.1](#).

The subset of AEs that are considered by the Investigator to be related to study drug will be considered to be treatment-related AEs. If the Investigator does not specify the relationship of the AE to study drug, the AE will be considered to be treatment-related. The incidence of AEs and treatment-related AEs will be tabulated.

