Summary of Proportion of Subjects with  $\geq 50\%$  Reduction from Baseline in Spleen Palpation Length  
by Study Week and Final Titrated Dose Group  
(Population: ITT Subjects)

NOTE TO THE PROGRAMMER: this table will be similarly program as Table 14.2.2.2 but will not derive/display reason of not achieving a response.

PROTOCOL: INCB 18424-258  
DRUG/INDICATION: Ruxolitinib/Myelofibrosis

(Page 1 of 1)  
VERSION: Final

Table 14.2.4.3

Summary of Proportion of Subjects with  $\geq 20\%$  Reduction from Baseline in Spleen Palpation Length  
by Study Week and Final Titrated Dose Group  
(Population: ITT Subjects)

NOTE TO THE PROGRAMMER: this table will be similarly program as Table 14.2.2.2 but will not derive/display reason of not achieving a response.

PROTOCOL: INCB 18424-258  
DRUG/INDICATION: Ruxolitinib/Myelofibrosis

(Page 1 of 1)  
VERSION: Final

Table 14.2.5.1

Summary of Patient Global Impression of Change Score by Study Week and Final Titrated Dose Group  
(Population: ITT Subjects)

NOTE TO THE PROGRAMMER: this table will be similarly program as Table 14.2.2.1 but no change and percent change will be derived.

PROTOCOL: INCB 18424-258  
DRUG/INDICATION: Ruxolitinib/Myelofibrosis

(Page 1 of 1)  
VERSION: Final

NOTE TO THE PROGRAMMER: this table will be similarly program as Table 14.2.2.1.

PROTOCOL: INCB 18424-258  
DRUG/INDICATION: Ruxolitinib/Myelofibrosis

(Page 1 of 1)  
VERSION: Final

NOTE TO THE PROGRAMMER: this table will be similarly program as Table 14.2.2.1.

PROTOCOL: INCB 18424-258  
 DRUG/INDICATION: Ruxolitinib/Myelofibrosis

(Page 1 of 3)  
 VERSION: Final

Table 14.3.1.1

Summary of Exposure and Duration of Exposure to Study Medication Through Week 24 by Final Titrate Dose Level  
 (Population: Safety Evaluable Subjects)

Variable	Ruxolitinib Final Titrated Dose (mg)				
	Total (N=xxx)	< 5 (N=xx)	>5 to 15 (N=xx)	>15 to 25 (N=xx)	>25 (N=xx)
Duration of Treatment (weeks) [1]					
n	xxx	xx	xx	xx	xx
Mean	xxxx.x	xxxx.x	xxxx.x	xxxx.x	xxxx.x
Std	xxxx.xx	xxxx.xx	xxxx.xx	xxxx.xx	xxxx.xx
Median	xxxx.x	xxxxx.x	xxxx.x	xxxx.x	xxxx.x
Min, Max	(xx.x, xx.x)	(xx.x, xx.x)	(xx.x, xx.x)	(xx.x, xx.x)	(xx.x, xx.x)
<=30 Days	xx (xx.x)	xx (xx.x)	xx (xx.x)	xx (xx.x)	xx (xx.x)
31-90 Days	xx (xx.x)	xx (xx.x)	xx (xx.x)	xx (xx.x)	xx (xx.x)
91-120 Days	xx (xx.x)	xx (xx.x)	xx (xx.x)	xx (xx.x)	xx (xx.x)
121-150 Days	xx (xx.x)	xx (xx.x)	xx (xx.x)	xx (xx.x)	xx (xx.x)
>150 Days	xx (xx.x)	xx (xx.x)	xx (xx.x)	xx (xx.x)	xx (xx.x)

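### EOT values that replace a scheduled visit are recovered for spleen length and spleen volume but not for PGIC or by-visit laboratory values, so those by-week rows omit subjects who stopped at that visit

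*SAP*

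**What the plan says.** Protocol 9.4 states: "If the EOT Visit coincides with a regular study visit, the end-of-treatment evaluations will supersede those of that scheduled visit". The data are then entered under the EOT visit. SAP 5.6 accepts the consequence: "if a subject's EOT Visit coincides with a scheduled visit, then in database, only EOT Visit data will be available".

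SAP 5.6 then treats variables in three ways:

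- **Spleen length.** "an effort will be made to see if the data actually falls into a scheduled visit", using the scheduled week x 7 ± 5 days.
- **Spleen volume.** If the matter is unresolved at database lock, "then similar effort will be made by treating spleen volume data labeled from" the EOT visit as unscheduled data. Under SAP 5.9.1 an unscheduled scan can serve as Week 24 if it falls on Day 141 to 175.
- **Other variables.** "The situation described above is not an issue of importance to other variables such as laboratory values". The reason given is that EOT appears as its own time point in analyses by time point.

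PGIC is not named in SAP 5.6. It is collected at EOT (Protocol 9.4 and Table 3), and Protocol 7.2.3 lists its change at each visit through Week 156 under the secondary endpoints. The SAP Appendix B shell is titled "Summary of Patient Global Impression of Change Score by Study Week and Final Titrated Dose Group" and carries no EOT rule. For hematology, Protocol 12.2.1 says: "Change in platelet count from baseline to each visit where the variables are measured will be tabulated with summary statistics". SAP 8.2 builds the by-visit laboratory tables from scheduled visits.

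**The concern.** The SAP's reason for leaving other variables alone does not meet the problem it has identified. A subject who stops at Week 12 and one who stops at Week 24 both land in the EOT row. That row says nothing about any given week, and its values cannot be added back to the week they belong to.

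Two things follow. The by-week PGIC, platelet and hemoglobin summaries leave out subjects seen on schedule, with values in hand, because they stopped that day. Spleen length at the same visit keeps those subjects, so two efficacy measures printed for one week rest on different populations. If those who stop at a visit tend to be doing poorly, the remaining subjects present a better picture than all attenders would.

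**Working it through.** **1. The plan's own figure.** Protocol 4.1.5 gives 53.7% much or very much improved on PGIC at Week 24 and 36.6% at Week 4. Among all fractions with denominators from 20 to 50, only 22/41 rounds to 53.7% and only 15/41 to 36.6%. The same section reports 33 subjects who completed Week 24 and 8 who discontinued before it; 33 + 8 = 41. The interim percentages therefore appear to keep the 8 in the denominator. This is inferred from the arithmetic, not stated.

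**2. How many values are affected in the core phase.** The documents do not say how many EOT visits coincide with a scheduled one. Assume the interim rate of stops before Week 24, 8/50 = 16%, applied to 150 subjects: 24 stops over six visits (Weeks 4, 8, 12, 16, 20 and 24).

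- Stops evenly spread: a ± 5-day window covers 11 of 28 days, so 24 x 11/28 = 9.4 fall in a window, or about 1.6 per visit.
- Every stop on a visit: 24/6 = 4 per visit.

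**3. Effect on by-week PGIC response.** Take 53.7% as the true rate among n = 150 and omit k subjects. If none of the k responded, the printed rate is 0.537n/(n − k). If all did, it is (0.537n − k)/(n − k).

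| k omitted | None responded | All responded |
|---|---|---|
| 1.57 | 54.3% (+0.6) | 53.2% (−0.5) |
| 4 | 55.2% (+1.5) | 52.4% (−1.3) |

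Using 150 at every visit is a simplification. With 130 attending and 4 omitted, the upper value is 0.537 x 130/126 = 55.4% (+1.7).

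**4. Stops at Week 24 itself.** Step 2 uses only the rate of stops before Week 24. Protocol 7.1 lets subjects receiving benefit continue, and the Table 14.1.1 shell counts completion of the treatment phase separately from entry to the extension. Some subjects may therefore attend Week 24 and stop there. If a fraction s does so and none is much improved, the printed rate is 53.7/(1 − s):

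- s = 5%: 56.5%, or +2.8 points.
- s = 10%: 59.7%, or +6.0 points.

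Both values of s are assumptions. Having no responders among those omitted makes each shift an upper limit for its s.

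**5. Platelets.** Omitting one subject at 25 x 10⁹/L from n subjects whose others average m raises the mean by (m − 25)/n. For assumed m of 50 to 100 and n of 41 to 50, this runs from 25/50 = 0.5 to 75/41 = 1.8 x 10⁹/L.

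**6. What the rule does not touch.** Total symptom score uses day windows (SAP 5.9.2), so the label is irrelevant. The laboratory CTCAE shift tables use all scheduled and unscheduled values (SAP 8.2). Grade 4 thrombocytopenia counts any treatment-emergent value below 25 (Table 14.3.3.6.1 shell).

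**The case against.** The strongest reply is that little is lost. Both co-primary endpoints and every secondary endpoint in SAP 3.1.2.3 are protected. The laboratory values still appear in the EOT row, the CTCAE shift tables, the Grade 4 counts and the listings. What remains is descriptive. This stands, and it limits the point to by-week PGIC and by-visit laboratory summaries.

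Three stronger readings are tempting, and the documents do not support them.

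- **Only spleen length is recovered.** SAP 5.6 also gives spleen volume a route.
- **The by-week rows are inflated.** Disposition reasons in the Table 14.1.1 shell include consent withdrawal, non-compliance and sponsor termination. Under SAP 4.1 treatment may run until commercial availability, so subjects still benefiting could also have EOT records. Only 1 of 50 interim subjects withdrew for thrombocytopenia. Away from Week 24 the direction is open.
- **The distortion is large.** One could start from 22 of 33 (66.7%) and suppose that 20% of Week 24 attenders stop there, none improved. That gives 66.7/0.8 = 83.3%, or 16.7 points. The base assumes that all 22 improved subjects completed Week 24. The 20% would be 20/33.3 = 60% of all non-responders stopping at one visit. Nor is 11/28 = 39% a lower limit on coincidence, since it counts EOT dates shortly after a scheduled visit that was already recorded.

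A practical objection also stands. A ± 5-day window cannot be applied to weekly hematology: Week 3 would span Days 16 to 26 and Week 4 Days 23 to 33, so one value could enter two rows.

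**Conclusion.** The inconsistency is real and follows from the text of Protocol 9.4 and SAP 5.6. Coinciding EOT values of PGIC and laboratory tests are collected but left out of the week they belong to, and the separate EOT row does not repair this. The omission may flatter the by-week rows. That is most plausible at Week 24, because continuation depends on benefit; at other visits neither direction is established.

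The documents do not fix the size. With 53.7% taken as the true PGIC rate, it is about 0.5 to 1.5 points in either direction at core visits. At Week 24 it is at most about 2.8 or 6.0 points if 5% or 10% of attenders stop there. The point deserves correction because the omission is selective and avoidable. It does not threaten the co-primary results or the Grade 4 thrombocytopenia endpoint.

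**What to change.** In SAP 5.6:

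- Extend the spleen-length rule to PGIC and to laboratory values at the main study visits (Weeks 4, 8, 12, 16, 20 and 24, then every 12 weeks). Assign the EOT value to the scheduled week when it falls within week x 7 ± 5 days, and only when no value is recorded for that scheduled visit.
- For laboratory-only weeks, use the ± 3-day window and assign each value to the single nearest scheduled visit, so that none enters two rows.
- Keep the EOT row as an additional row.
- Delete the sentence that calls the matter unimportant for other variables.

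The cost is minor programming, mostly reuse of an existing derivation plus the nearest-visit step for laboratory-only weeks. No new data are needed. By-week results may turn out slightly less favourable.

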## **5.7. Concomitant Medications and Partial Dates**

Prior medication is defined as any non-study medication started prior to the date of first study drug administration.

Concomitant medication is defined as any non-study medication that is:

- Started before the date of first study drug administration and is ongoing throughout the study or ends on/after the date of first study drug administration;
- Started on/after the date of first study drug administration and is ongoing or ends during the course of study medication.

A prior medication could also be classified as "both prior and concomitant medication" if the end date is on or after first dose of study medication. In the listing, it will be indicated whether or not a medication is prior-only, concomitant-only, or both prior and concomitant medication.

The start/stop dates recorded by the Investigator and his/her research staff in the eCRF will be used to identify when a concomitant medication was taken during the study. Any missing start date must be queried for resolution. Unresolved missing start dates will be handled according to the following order of steps.

- If the date is completely missing, the medication will be considered both prior and concomitant.
- If only the day is missing, and the last day of the month is prior the first dose date on Day 1, then the concomitant medication will be considered as starting prior to Day 1, and the incomplete date will be handled as if it is the last day of the month.
- If only the day is missing, and the first day of the month is after the first dose date on Day 1, then the concomitant medication will be considered as starting after Day 1, and the incomplete date will be handled as if it is the first day of the month.
- If only the day is missing, and the month is equal to the month of the first dose date on Day 1, then the missing day will be handled as if it is the first day of the month.
- If both the month and day are missing, and the last day of the year is prior to the first dosing date on Day 1, then the concomitant medication will be considered as starting before Day 1, and the incomplete date will be handled as if it is the last day of the year. Otherwise, the missing date will be handled as if it is the first day of the year.

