7. Subjects who have platelet counts between 50 and 100 x 10⁹/L at the screening and/or baseline visits. Platelet counts must be without the assistance of growth factors, thrombopoietic factors, or platelet transfusions.
8. Subjects with hemoglobin value at the screening visit ≥ 6.5 g/dL and who are willing to receive red blood cell transfusions to treat low hemoglobin levels.
9. Subjects must have discontinued all drugs used to treat underlying MF disease no later than Day -14.
10. Subjects must not currently have the option of stem cell transplantation, either because they are not a candidate, or because a suitable donor is not available.
11. Subjects with an ECOG performance status of 0, 1, 2 or 3 ([Appendix 5](#)) at the screening visit.
12. Subjects with peripheral blood blast count of < 5% at both screening and baseline visits.

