8.9.2. Prohibited Medications and Measures

- Any prior or concomitant use of another JAK inhibitor.
- Any investigational medication other than the study drugs. Use of such medications within 14 days or 6 half-lives, whichever is longer, prior to the first dose of study drug and during the study through the follow-up visit is prohibited.
- Systemic corticosteroid doses greater than the equivalent of 10 mg prednisolone per day are not permitted, unless use is part of a ruxolitinib dose tapering strategy (see [Section 8.6.6](#) Optional Dose Tapering Strategy).
- Romiplostim or eltrombopag are not permitted beginning with the baseline visit (Day -7) through the final dose of ruxolitinib.
- St John's Wort and rifampin are not permitted at any time during participation in the study.
- Use of hydroxyurea, interferon, thalidomide, busulfan, lenalidomide, anagrelide, or any investigational medication used to treat MF is not permitted at any time beginning on Day -14 up until the time that ruxolitinib therapy is permanently discontinued. Use of androgens to treat anemia is permitted.

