## **5.8. Adverse Events and Missing Data**

A treatment-emergent adverse event (TEAE) is any AE either reported for the first time or worsening of a pre-existing event after first dose of study medication. Analysis of AEs will be limited to TEAEs, but data listings will include all AEs.

Severity of AEs will be described and graded using the National Cancer Institute (NCI) Common Terminology Criteria for Adverse Events (CTCAE). CTCAE v4.03 is used for this protocol. If the toxicity is not included in the CTCAE v4.03 criteria it will be rated on a 1 to 4 scale as follows: mild = 1; moderate = 2; severe = 3; and life-threatening = 4.

An AE will also be assessed by its relationship to study medication as well as by seriousness. These assessments will be directly from data collected on eCRFs and are described in details in the protocol.

Any missing onset date, causality, or severity must be queried for resolution. Unsolved missing values will be handled according to the following rules:

- An unsolved missing causality will be considered treatment related
- An unsolved missing severity will be identified as an unknown severity

- For purposes of analysis, all AEs will be considered TEAEs unless the AE can unequivocally be defined as not treatment emergent. Therefore, an unsolved missing onset date will be considered treatment emergent, with the following examples illustrating exceptions:
  - If the stop/resolution date is before the first dose date on Day 1, then the AE will be considered as not being treatment emergent.
  - If both the month and day are missing, and the last day of the year is before the first dose date on Day 1, then the AE will not be considered treatment emergent.
  - If only the day is missing, and the last day of the month is before the first dose date on Day 1, then the AE will not be considered treatment emergent.
  - If only the day is missing, and the first day of the month is after the first dosing date on Day 1, then the AE will be considered treatment emergent.

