**9.3. Concomitant Medication**

CYP3A4 inhibitors and inducers may be tested as time dependent variables of variability if more than 15% of patients will take them as concomitant medications.

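### SAP 5.7 counts a medication with no start date as concomitant even when its recorded stop date is before Day 1, and its definition for drugs begun on treatment can be read two ways

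*SAP*

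**What the plan says.** SAP 5.7 first defines the terms. A drug begun before first dose is concomitant only if it is still in use at, or ends on or after, first dose. The section repeats this test for a prior drug that is to count as both: "if the end date is on or after first dose of study medication". A drug begun on or after first dose is concomitant under a second bullet: "Started on/after the date of first study drug administration and is ongoing or ends during the course of study medication".

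Missing start dates must be queried. Then: "Unresolved missing start dates will be handled according to the following order of steps". The first step is: "If the date is completely missing, the medication will be considered both prior and concomitant". The later steps impute partial start dates to a first or last day of the month or year.

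SAP 5.8 treats missing adverse event (AE) onset dates just as cautiously but makes an exception: "If the stop/resolution date is before the first dose date on Day 1, then the AE will be considered as not being treatment emergent".

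The classification is used in SAP 6.7, which summarises concomitant medications (Table 14.1.5.2) and flags each listed record as prior, concomitant or both (Listing 16.2.4.3).

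**The concern.** A drug whose recorded stop date is before Day 1 cannot have been taken with ruxolitinib, whatever its start date. The first imputation step nevertheless calls it concomitant.

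The pattern is plausible here. Inclusion criterion 9 says: "Subjects must have discontinued all drugs used to treat underlying MF disease no later than Day -14". Protocol 8.8 records medication taken up to 30 days before the baseline visit, and Protocol 9.1.1 has sites record the history of MF drugs. A washed-out MF drug is therefore in the data, and a long-standing one may lack a start date.

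The second bullet matters at the other end of treatment. Protocol 8.9.2 bars the listed MF drugs for a limited period, so that use "is not permitted at any time beginning on Day -14 up until the time that ruxolitinib therapy is permanently discontinued". Protocol 9.5 reviews concomitant medications again 30 to 37 days later. Protocol 8.6.6 allows corticosteroids to be started before or during a ruxolitinib taper. Drugs that begin after the last dose, or that straddle it, are thus foreseeable.

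The trial is open label and single arm (Protocol 8.3). A reader who looks in the concomitant medication table for other MF therapy or steroids should find what was actually taken with ruxolitinib.

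**Working it through.** The plan states no figure on this point, so there is none to reproduce. The check applies the SAP 5.7 rules to date patterns. The last dose is set at Day 168 for illustration (an assumption).

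Two readings of the second bullet are used:
- Reading A: ongoing stands alone as a status, and only the end date is tied to the course of study medication.
- Reading B: the phrase about the course of study medication governs both verbs, so a drug in use at any time during that course qualifies.

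| Case | Start | Stop | Reading A | Reading B | Days taken with ruxolitinib |
|---|---|---|---|---|---|
| 1 | completely missing | Day -14 | prior and concomitant | prior and concomitant | 0 |
| 2 | known, Day -400 | Day -14 | prior only | prior only | 0 |
| 3 | year only | Day -14 | prior only | prior only | 0 |
| 4 | 10 days after last dose | ongoing at follow-up | concomitant only | neither | 0 |
| 5 | 10 days after last dose | 20 days after last dose | neither | neither | 0 |
| 6 | Day 100 | 10 days after last dose | neither | concomitant only | 168 - 100 + 1 = 69 |
| 7 | year only, Day 1 year; truly after last dose | 20 days after last dose | prior and concomitant | prior and concomitant | 0 |

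**Case 1** is wrong on both readings. Cases 2 and 3 have the same stop date and are classed correctly, because imputing a partial date changes only the start and the ordinary end-date test then applies. The error in case 1 therefore belongs to the completely missing start date alone.

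**Cases 4 and 6** depend on the reading. A includes a drug with no overlap and omits one with 69 days of overlap; B gets both right. For case 6 this requires ongoing to mean in use during the course. If a programmer takes it as the status recorded at data collection, case 6 remains in neither class. A shorter example: a steroid given from Day 150 to Day 180 with last dose on Day 165 overlaps for 165 - 150 + 1 = 16 days, and reading A omits it.

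**Comparison of the two bullets.** The bullet for drugs begun before Day 1 sets no upper limit on the end date. A drug begun on Day -1 and ending after the last dose is concomitant. Under reading A, one begun on Day 1 with the same end date is not.

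**Case 5** shows that a post-treatment drug with a known start that has also ended is not counted on either reading.

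**Case 7** is a separate, smaller gap: imputation to 1 January moves a post-treatment drug to before Day 1.

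**The case against.** The strongest reply is that the first step is a cautious default for a rare event. It applies only when no part of the start date is known and a mandatory query has failed, and Protocol 9.1.1 already asks sites to record prior MF medication. This is fair on frequency. It does not defend the rule: SAP 5.8 is equally cautious and still respects a known stop date.

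On the second bullet, reading B is grammatically natural and removes both problems. That stands, so the bullet is ambiguous rather than wrong. It still needs rewording, because two programmers could code it differently.

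A reader might infer more than the documents support:
- *That washed-out and post-treatment MF drugs are generally counted as concomitant.* They are not. Any recorded start year brings the stop date back into play. A post-treatment drug with a known start is counted only under reading A, and only if still ongoing.
- *That the flag drives the CYP3A4 covariate rule in SAP 9.3*, which tests inhibitors and inducers "if more than 15% of patients will take them as concomitant medications". SAP 9.3 does not cite 5.7, and a time-dependent covariate needs actual dates rather than a prior or concomitant flag. The link is not shown.
- *That the table is the plan's safeguard against prohibited therapy.* Deviations are logged by monitors (Protocol 14.2) and listed (SAP 6.3). Prior MF therapy has its own listing (16.2.4.4), and the documents do not settle whether it also enters the concomitant table.

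**Conclusion.** The point holds in a narrow form and is minor. The rule for a completely missing start date contradicts SAP 5.7's own definition and gives a wrong entry whenever the recorded stop date is before Day 1. This conclusion does not depend on how the second bullet is read. The second bullet is ambiguous, and one of its two readings misclassifies drugs around the last dose.

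The effect is limited to Table 14.1.5.2 and the listing flags. The co-primary correlations do not use the classification. Per-protocol membership comes from compliance and monitored deviations (SAP 5.9.6). The number of subjects affected cannot be estimated, because the documents give no rate of start dates that remain wholly missing after query; any count would only restate an assumed rate.

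**What to change.** Make these changes in SAP 5.7:
1. Before any start-date imputation, class a medication whose known stop date is before Day 1 as prior only, in line with SAP 5.8.
2. Replace the two definition bullets with one rule: concomitant means a stop date on or after first dose (or ongoing) and a start date on or before last dose.
3. Flag medications begun after the last dose as post-treatment and tabulate them separately.

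With these changes case 1 becomes prior only, cases 4 and 5 become post-treatment, and case 6 becomes concomitant. A wholly missing start with a later or unknown stop keeps the cautious default. Case 7 is not cured, because the imputed start of 1 January still precedes the last dose; a footnote identifying imputed start dates would make such records visible.

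The cost is a few sentences in the SAP and one changed derivation. No new data are needed.
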